8.1 Primary end point

A completed questionnaire on patient's demographic and medical illness data, stool output/day, stool consistency per output/day and constipated related symptoms scoring/day over the period of 7 study days.

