8.2 Safety

Patients will be counseled that generally safety profile of probiotics seems to be good. Based on the available trials, no adverse effects were noted. There might be a concern issue of safety in immune-compromised patients or those critically ill, which they will be excluded in this study.

Patients will be withdrawn from the study if they experience intolerable or any possible excessive side effects due to probiotics.

9. Assessment variables and methods of assessing.

9.1 Targeted patients will be assessed with a questionnaire (Appendix C) on gastrointestinal symptoms, well-being and stool habits. The stool consistency will be scored by a seven-point scale according to the Bristol Stool Form Scale (Appendix B). Severity of constipation will be categorized into four groups (severe, moderate, mild and no symptoms). Symptoms specifically

related to constipation such as bloating and flatulence will be recorded in detail. Severity of symptom is measured by Likert score of frequency (Very frequently, frequently, occasionally, rarely and never).

9.2 Each individual patient will be required to fill in the questionnaire at the beginning of the trial. Subsequently, patient will be required to fill up the stool chart and recorded their symptoms in a given dairy daily during the study period. Training on how to use and record the dairy will be conducted upon embarking into the study. A contact number will be advised to the participants to aid their understanding. The dairy will be collected at day 7 upon completion of the study.

Other assessment

1. Assessment of the presence of underlying medical illness will be done at the initial presentation, assessed by questionnaire about the medical history and physical examination.

10. Study conduct

10.1 Elderly patients attending medical/surgical clinics or being admitted to the medical/surgical wards PPUKM will be screened. Those with underlying medical illnesses and suspected to have constipation are selected. Random selection of the participants either for intervention group or control will be pre-determining during screening.

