APPENDIX D

[figure not shown]
EVALUATING THE EFFECT OF PROBIOTICS IN CHRONIC CONSTIPATION ELDERLY PATIENTS WITH MULTIPLE CO-MORBIDITIES

QUESTIONNAIRES

[figure not shown]
Study Number:

Patient's Sticker:

[figure not shown]
1. How frequent is your bowel movements per week?

[figure not shown]
2. Do you need assistance in evacuation? (enema/digital-manual maneuvers)

[figure not shown]
3. Do you have sensation of anorectal obstruction/ blockage?

[figure not shown]
4. Feeling of incomplete evacuation?

[figure not shown]
5. Do you have lumpy or hard stools?

[figure not shown]
6. Any straining or squeezing on defecation attempts?

[figure not shown]
1. How long have you had constipation?

[figure not shown]
2. Do you have bloating in your stomach?

[figure not shown]
3. Do you have flatulence?

[figure not shown]
4. Do you have stomach cramps?

[figure not shown]
5. How many unsuccessful attempts of evacuation within 24hours?

6. Do you have abdominal pain?

7. How long do you spend in the lavatory per attempt? (minutes)

Statistical analysis Plan

The collected data was analysed using IBM SPSS Statistics for Windows version 21.0 software (IBM Corp., Armonk, NY, USA) and Microsoft Office Excel 2010software (Microsoft, Redmond, WA, USA). Statistical significance was set at $p = <0.050$.

All of the data was assessed for normality via the usual processes.

The baseline characteristic differences between the two groups were evaluated using the Mann-Whitney U and chi-squared tests. The median results of the improvement in stool frequencies and stool consistency between the treatment and placebo group were compared using the Mann-Whitney U test. The constipation-related symptom improvements were analysed using the chi-squared test.

Intention to treat analysis was used in this trial, where only the final results within the group which they were randomized, receiving the treatment and completed the treatment assignment were analysed. Participants who deviates from the protocol as being non-compliance or withdrew consent were not included into the analysis.

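### The primary end point is a whole questionnaire, and at least three efficacy outcomes are tested at p<0.050 with no rule for which one decides the trial

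*Combined protocol and SAP*

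**What the plan says.** Protocol section 8.1, headed as the primary end point, names a completed questionnaire. It holds demographic and medical-illness data together with "stool output/day, stool consistency per output/day and constipated related symptoms scoring/day over the period of 7 study days". No single variable is picked out, and nothing says how seven daily values become one value per patient.

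The Statistical analysis Plan, which follows Appendix D, gives one threshold for everything: "Statistical significance was set at" p<0.050. It then lists the efficacy comparisons:

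- Stool frequency and stool consistency: "improvement in stool frequencies and stool consistency between the treatment and placebo group were compared using the Mann-Whitney U test".
- Symptoms: "The constipation-related symptom improvements were analysed using the chi-squared test".

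Section 9.1 adds that "Severity of symptom is measured by Likert score of frequency", on five levels, and that "Severity of constipation will be categorized into four groups". The SAP does not say whether symptom improvement is analysed as yes or no, or whether there is one symptom test or several.

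Neither the protocol nor the SAP states a primary test, a testing order, a requirement that several outcomes all succeed, or a multiplicity adjustment. Section 6 mentions a sample size calculation but does not show it, so it cannot reveal which variable was intended as primary.

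**The concern.** A questionnaire is a data collection instrument; it is not an outcome that can be compared between two groups. Demographic and medical-history items describe patients at entry and cannot measure efficacy. That leaves three efficacy domains of equal standing, each with its own test and no rule for combining the results.

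The trial therefore has no defined success criterion. If one of the three comparisons falls below 0.050 and the others do not, the plan does not say whether probiotic has been shown to work. Nothing in it prevents the significant result from being presented as the main finding, and that choice could be made after the data are seen. The false-positive risk attached to an efficacy claim is then larger than the stated threshold suggests.

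**Working it through.** The documents give no familywise error rate, so there is no figure of the plan's own to reproduce.

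**Inputs from the documents.** Two groups (section 7), so one between-group comparison per outcome. Threshold 0.050 (SAP). Efficacy tests: frequency, consistency and at least one symptom test (SAP), so k = 3 as a minimum. Baseline comparisons are not efficacy tests and are not counted.

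**Assumptions, none stated in the documents.** Tests are two-sided, so 0.025 lies in the direction favouring probiotic. The 0.05 applies to each test. There is no true effect on any outcome. Any one significant result is read as efficacy. For the correlated and directional figures, the test statistics are approximately normal with 1 degree of freedom and have equal pairwise correlation ρ, shown at 0, 0.5 and 0.9.

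**Independent tests (ρ = 0).**

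- Any direction: 1 − 0.95³ = 1 − 0.8574 = 0.1426.
- Favouring probiotic: 1 − 0.975³ = 1 − 0.9269 = 0.0731.

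**Correlated tests.** With critical value c = 1.96, φ and Φ the standard normal density and distribution function, and x the shared factor:

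- Favouring probiotic: 1 − ∫ φ(x) · [Φ((c − √ρ·x)/√(1−ρ))]³ dx.
- Any direction: 1 − ∫ φ(x) · [Φ((c − √ρ·x)/√(1−ρ)) − Φ((−c − √ρ·x)/√(1−ρ))]³ dx.

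| | ρ = 0 | ρ = 0.5 | ρ = 0.9 | One test |
|---|---|---|---|---|
| Favouring probiotic | 7.3% | 6.3% | 4.2% | 2.5% |
| Any direction | 14.3% | 12.5% | 8.4% | 5% |

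A simulation of 4 million draws gave 6.27% and 12.53% at ρ = 0.5, and 4.18% and 8.36% at ρ = 0.9, in agreement. Relative to one test, the favouring rate is 7.3/2.5 = 2.9 times as large at ρ = 0 and 4.2/2.5 = 1.7 times at ρ = 0.9.

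**After the fix.** With one primary test acting as gatekeeper, the rates return to 5.0% in any direction and 2.5% favouring probiotic. With Holm across three tests, the any-direction rate is 4.9% at ρ = 0 and 3.0% at ρ = 0.9.

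**Cost in power.** The first Holm step for three tests is 0.05/3 = 0.0167. A comparison with 80% power at two-sided 0.05 has expected statistic 1.960 + 0.8416 = 2.8016. The two-sided 0.0167 critical value is 2.394. Power at that step is Φ(2.8016 − 2.394) = Φ(0.408), about 66%.

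**The case against.** The strongest defence is that the three efficacy domains in section 8.1 are the same three that the SAP tests, each with a named method. That is right, and it narrows the point: the outcomes and tests are laid down, and what is missing is the rule that turns three results into one conclusion. The error rates also depend on reading any single success as efficacy. If all three had to succeed, the false-positive rate could not exceed the 5% of a single test. The documents state neither rule, so the inflation is what the plan permits, not what it declares.

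A reader might go further in three ways that the documents do not support.

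- One could count the diary's four named symptom columns plus its open column in Appendix B and conclude that six or seven efficacy tests are planned. Separate symptom tests would raise the rates above, but the SAP gives no number of symptom tests. The diary columns establish neither that count nor an upper limit, since Appendices C and D list further symptoms. Only the minimum of three is documented.
- One could treat two-sided testing, and the 2.5% benchmark with it, as stated. The SAP gives only the threshold; two-sidedness is the natural reading but an assumption.
- One could infer that an outcome was in fact chosen after the data were seen. Nothing shows this. The past tense of the SAP ("The collected data was analysed using") leaves its timing relative to unblinding unclear and proves no more.

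Finally, the correlation between the tests is unknown, and outcomes in the same patients are probably related. The table allows for this: correlation reduces the excess but does not remove it.

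**Conclusion.** The concern stands. Section 8.1 does not define a primary end point that can be tested, and the SAP gives at least three unadjusted chances of a positive efficacy claim. The favouring-probiotic and any-direction rates in the table stay above their single-test benchmarks at every correlation shown. The direction of the conclusion does not depend on the assumed correlation; its size does.

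The figures rest on the five assumptions listed in the working. The any-direction figure under independence does not need the 1-degree-of-freedom assumption; the others do, and that assumption fits best if symptoms are analysed as improved or not improved. This should be fixed before any efficacy result is interpreted, because without it the trial has no stated criterion for success.

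**What to change.** **If the data are still blinded:**

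- Replace section 8.1 with one primary efficacy variable and state how the seven days are summarised for each patient. Test it two-sided at 0.05. It should be the variable behind the sample size calculation mentioned in section 6.
- Remove demographic and medical-history data from the end point.
- List the remaining stool and symptom outcomes by name as secondary, stating how symptom improvement is scored. Test them, with Holm adjustment, only if the primary is significant. Alternatively, apply Holm across all named efficacy tests.

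**If the data are already unblinded,** do not promote one outcome to primary. Report all efficacy comparisons, with Holm across the full set that was run, or label them exploratory.

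**Cost.** The change is to protocol and SAP text, plus a check that the chosen primary is adequately powered under the sample size calculation. The downside is stricter thresholds for the other outcomes. With a gatekeeping primary and two secondaries, the first Holm step is 0.05/2 = 0.025. With Holm across three tests it is 0.0167, where a comparison with 80% power at 0.05 keeps about 66%. Naming one primary avoids that loss for the outcome that matters most.

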8.2 Safety

Patients will be counseled that generally safety profile of probiotics seems to be good. Based on the available trials, no adverse effects were noted. There might be a concern issue of safety in immune-compromised patients or those critically ill, which they will be excluded in this study.

Patients will be withdrawn from the study if they experience intolerable or any possible excessive side effects due to probiotics.

9. Assessment variables and methods of assessing.

9.1 Targeted patients will be assessed with a questionnaire (Appendix C) on gastrointestinal symptoms, well-being and stool habits. The stool consistency will be scored by a seven-point scale according to the Bristol Stool Form Scale (Appendix B). Severity of constipation will be categorized into four groups (severe, moderate, mild and no symptoms). Symptoms specifically

related to constipation such as bloating and flatulence will be recorded in detail. Severity of symptom is measured by Likert score of frequency (Very frequently, frequently, occasionally, rarely and never).

9.2 Each individual patient will be required to fill in the questionnaire at the beginning of the trial. Subsequently, patient will be required to fill up the stool chart and recorded their symptoms in a given dairy daily during the study period. Training on how to use and record the dairy will be conducted upon embarking into the study. A contact number will be advised to the participants to aid their understanding. The dairy will be collected at day 7 upon completion of the study.

Other assessment

1. Assessment of the presence of underlying medical illness will be done at the initial presentation, assessed by questionnaire about the medical history and physical examination.

10. Study conduct

10.1 Elderly patients attending medical/surgical clinics or being admitted to the medical/surgical wards PPUKM will be screened. Those with underlying medical illnesses and suspected to have constipation are selected. Random selection of the participants either for intervention group or control will be pre-determining during screening.

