Subjects will be withdrawn from the study in the event of:

1. Consent is withdrawn by the patient.
2. Patients will be withdrawn from the study if they experience intolerable or excessive side effects due to the probiotics.

Subject drop out is predicted at 10% and is taken into consideration in the sample size calculation.

7. Study Intervention

Patient will be randomized into a treatment or control group. No other treatments such as laxatives or enemas are given to all patients.

1. Treatment group.
 - a. Each patient will receive probiotics in form of granular powdered microbial cell preparation (Hexbio®) – Specialized formulation of six microbial strains containing:
 - i. Lactobacillus acidophilus BCMC® 12130
 - ii. Lactobacillus casei BCMC® 12313
 - iii. Lactobacillus lactis BCMC® 12451

- iv. Bifidobacterium bifidum BCMC® 02290
- v. Bifidobacterium infantis BCMC® 02129
- vi. Bifidobacterium longum BCMC® 02120

b. Dosage: 1 sachet twice a day after meals for 1 week.

2. Control group

- a. Each patient will receive placebo sample of similar appearance and composition but do not contain probiotics.

8. Efficacy, Safety and Other Assessments

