APPENDIX B

DAILY STOOL DIARY						LIKERT SCALE / NUMERIC PAIN RATING SCALE							
Study No: _____ Patient's Sticker: _____ EVALUATING THE EFFECT OF PROBIOTICS IN CHRONIC CONSTIPATION ELDERLY PATIENTS WITH MULTIPLE CO-MORBIDITIES													
DAY	CONSTIPATION RELATED SYMPTOMS					BRISTOL STOOL CHART							
	STRAINING	PAINFUL EVACUATION	BLOATING & FLATULENCE	STOMACH CRAMPS	OTHERS		TYPE 1	TYPE 2	TYPE 3	TYPE 4	TYPE 5	TYPE 6	TYPE 7
BEFORE													
1													
2													
3													
4													
5													
6													
7													

Instructions: Please fill up the boxes according to likert scale for the constipation related symptoms and mark 'X' for the Bristol stool chart.

Bristol chart adapted from http://www.cbc.ca/stevenandchris/content/images/poop_101_1.jpg

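### Safety is a named assessment, but the visible forms do not collect adverse events systematically and the SAP plans no safety analysis, so a complete adverse-event result by arm cannot be produced as planned.

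*Combined protocol and SAP*

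**What the plan says.** Section 8 of the protocol is headed "Efficacy, Safety and Other Assessments", so safety is a declared assessment alongside efficacy. Section 8.2 tells patients about the product's safety record ("Based on the available trials, no adverse effects were noted"), notes that immune-compromised and critically ill patients are excluded, and gives one operational rule: "Patients will be withdrawn from the study if they experience intolerable or any possible excessive side effects due to probiotics". Section 6 has a similar rule.

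During treatment, section 9.2 provides for a diary: "patient will be required to fill up the stool chart and recorded their symptoms in a given dairy daily during the study period". The diary in Appendix B has a BEFORE row and rows for days 1 to 7. Its five complaint columns (straining, painful evacuation, bloating and flatulence, stomach cramps, OTHERS) all sit under "CONSTIPATION RELATED SYMPTOMS", beside Bristol types 1 to 7. The instruction to the patient is: "Please fill up the boxes according to likert scale for the constipation related symptoms and mark 'X' for the Bristol stool chart".

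The SAP lists comparisons of baseline characteristics, stool frequency, stool consistency and improvement in constipation symptoms. It limits the analysis to patients who received and completed their assigned treatment, and adds: "Participants who deviates from the protocol as being non-compliance or withdrew consent were not included into the analysis".

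**The concern.** An assessment that is named but has no collection form, no analysis population and no table is not really planned. An event that nobody asks about during the seven days cannot be recovered at analysis. The participants are aged 60 or over with at least two chronic illnesses, and some are inpatients, so intercurrent complaints are to be expected in both arms and need a comparison by arm to be interpreted.

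The withdrawal rule and the analysed set also work against each other. The rule removes patients because of side effects, and the SAP then analyses only those who finished. The patients most informative about tolerability are the ones missing from the only set the SAP defines. A report written to this plan could present an efficacy result with no adverse events listed, and a reader could take that as evidence that there were none.

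**Working it through.** The plan states no figure on this point, and there is no sample size, allocation ratio or event rate from which to derive one. The check is therefore a comparison of the sections.

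**1. Is safety meant to be assessed?** Yes, by the heading of section 8 and the existence of section 8.2.

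**2. Does section 8.2 say how?** No. It does not define an adverse event or say how events are asked about, graded, attributed or reported. The withdrawal rule depends on the side effect being due to the probiotic. Section 1 describes the trial as double-blind, and no procedure for that attribution is given.

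**3. Which visible forms could record an on-treatment event?**

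| Form | When completed | Relevant content |
|---|---|---|
| Appendix B, diary | BEFORE and days 1-7 | Five complaint columns, all labelled constipation-related; Bristol types 1-7 |
| Appendix C, data collection form | Enrolment, by its content (demographics, history) | No adverse-event field |
| Appendix D, questionnaire | Start of trial (sections 9.2 and 10.4) | Constipation, bloating, flatulence, cramps, pain; no on-treatment use described |

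Only the diary covers the treatment period. It captures stomach cramps, bloating and flatulence, and loose stools (types 6-7), each against a baseline row. OTHERS is the nearest thing to an open field, but its heading and the instruction ask for constipation symptoms. A dizzy spell or a rash has no natural place there, and an entry cannot be separated from the condition under treatment. No form has a field for the reason for stopping. Section 9.2 offers a contact number to help patients understand the diary, not to report complaints. Sections 9.2 and 10.5 describe collecting the diary on completion at day 7, and nothing is said about retrieving it from a patient who stops earlier.

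**4. What does the SAP analyse?** Four items: baseline, stool frequency, stool consistency and symptom improvement. Safety analyses among them: 0 of 4. Worsening of a symptom is not mentioned, and the coding of improvement is not defined.

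**5. Who is analysed?** Completers. A patient withdrawn under section 6 or 8.2 has not completed treatment and so falls outside. No separate safety set is defined. Section 6 predicts 10% dropout, which is about 1 patient in 10. The share of that due to side effects is not stated, so within the predicted figure it could lie anywhere from 0% to 10% of patients. No visible form would show where.

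**6. What could still be reported by arm?** Counts of withdrawals, because patients are randomised, and worsening or new entries in the diary columns listed in step 3. Neither is planned, so both would be ad hoc.

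**The case against.** The strongest reply is that the trial does collect relevant data. The effects most plausible for an oral gut product are cramps, bloating, flatulence and loose stools, and the diary records these daily against a baseline. Withdrawals for side effects are provided for and can be counted by arm. The completer restriction governs which results are analysed; it does not delete records. The sentence in "Participants who deviates from the protocol as being non-compliance or withdrew consent were not included into the analysis" names non-compliance and withdrawn consent, not side effects. It is the preceding completer wording that excludes patients withdrawn for side effects.

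All of this stands, and it limits the point. A reader might infer that the plan yields no adverse-event data at all, or that no safety result by arm is possible. The documents do not support either reading, because the diary entries and withdrawals could be tabulated. For the same reason, an upper bound on the event rate from zero events would not measure the gap: it would need an arm size the documents do not give, and it treats the problem as total absence of capture.

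A further limit is that the flow chart, the figures in Appendix D and the consent form (Appendix E) are not shown. That no form collects adverse events is a judgement on the visible text. The missing SAP analysis does not depend on those pages.

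What the reply does not answer is that events outside the gut are not sought, reasons for stopping have no form, and no safety analysis is pre-specified.

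**Conclusion.** The point holds as a gap in systematic collection and in pre-specified analysis. Safety is a stated assessment, but the visible forms seek only constipation-related complaints, the SAP contains no safety analysis, and its only analysed set drops patients withdrawn for side effects. A complete adverse-event result by arm cannot be produced as planned; a partial, unplanned one could.

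The size is qualitative: no safety item among four listed analyses, one on-treatment form restricted to constipation symptoms and stool form, and an unrecorded reason behind a predicted 10% dropout. The conclusion assumes that the pages not shown contain no adverse-event form.

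The gap does not itself invalidate the efficacy comparison, and nothing in the documents indicates that the product caused harm. A change should be made because it is cheap and alters what the trial can say about tolerability.

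**What to change.** - **Diary:** add a daily column for any new or worse complaint, placed apart from the constipation symptoms.
- **Day-7 collection:** add a short page for adverse events, seriousness and, where it applies, the reason for stopping. Complete it, and collect the diary, for patients who stop early as well.
- **SAP:** define a safety set of everyone who took at least one sachet, including those who stopped. Add one descriptive table by arm with counts, percentages and confidence intervals for any event, serious events, withdrawals for side effects, worsening from BEFORE on each diary symptom, and change to Bristol types 6-7. No hypothesis test is needed.

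The cost is one diary column, one page, one table and a few minutes per patient at a contact that already exists. No efficacy analysis changes.

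The SAP is written in the past tense. If the diaries are already in, only the withdrawal counts and the diary-based rows can be produced. The report should then label them post hoc and state that other adverse events were not systematically sought.
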